3 DATA PROCESSING

All the data are processed using Analyst software version 1.6.2 associated with the mass spectrometer. Calibration curves are constructed by plotting the peak area ratio of Levofloxacin, Dexamethasone 21-phosphate and Dexamethasone to IS against the theoretical concentration of the analytes.

The concentration values in the study samples are directly calculated by the software using an optimal calibration curve defined during the method validation. Integration will be performed by the software or manually by the operator if the peak shape is anomalous or if the baseline is noisy. The manual integration is reported on the summary table elaborated by the software in the column "record modified", according to the TicinumLab SOP GCP004.

Code: GCLP022/01

Page. 18 of 27

4 METHOD VALIDATION

4.1 SELECTIVITY

Selectivity is the ability to differentiate the analyte of interest and the IS from the endogenous components in the matrix or other component in the sample.

4.1.1 Procedure

Analyse 6 different samples in matrix at LLOQ level and compare with of blank artificial aqueous humor (AHA) to verify the interferences with analytes and IS.

4.1.2 Calculation

Absence of interfering components is accepted if the mean response in blank is \leq 20% of the LLOQ for the analytes and \leq 5% for the IS.

4.2 LINEARITY

The linearity of an analytical procedure is its ability (within a given range) to obtain results which are directly proportional to the concentration (amount) of analyte in the sample.

4.2.1 Procedure

Prepare working standard solutions and IS working standard solutions as described in §2.3.1, 2.3.3 and the AHA samples as described in §2.4.1, process the samples as described in §2.4.2

Prepare a blank sample (only blank AHA sample processed) and a zero blank (blank AHA sample processed with internal standard). Inject the samples as described in the following sequence:

N.	SAMPLE
1	Blank
2	Zero blank
4	G
5	F
6	Е
7	D
8	C
9	В
10	Α

Code: GCLP022/01

Page. 19 of 27

4.2.2 Calculation

Determine the calibration curve that better link nominal analytes AHA concentration to the peak area ratio analyte / internal standard.

Linear or quadratic regression may be used and appropriate weighting factors may be explored and justified, however this weighting factor must be consistent throughout the study.

Evaluate the goodness of the fitting by linear correlation coefficient (r), this should be greater than 0.99.

The back calculated concentrations of CC standards should be within $\pm 15\%$ of the nominal value, except for LLOQ for which it should be $\pm 20\%$. At least 75% of CC must fulfill this criterion. Linearity is evaluated on at least three calibration curves.

4.3 CARRY-OVER EFFECT

Carry-over effect is assessed by injecting blank AHA sample after CC sample at the ULOQ.

4.3.1 Procedure

Prepare and inject blank AHA sample after CC sample at the ULOQ.

4.3.2 Calculation

Absence of carry-over effect is accepted where the response is $\leq 20\%$ of the LLOQ for the analytes, and $\leq 5\%$ for the internal standard.

4.4 LOWER LIMIT OF QUANTITATION (LLOQ)

The lower limit of quantitation is the lowest amount of analyte in a sample which can be quantitatively determined whit suitable precision and accuracy.

The analytical signal of LLOQ should be at least 5 times the signal of the blank sample and it should have accuracy and precision within \pm 20% in within-run assay and between-run assay as described in §4.5.

4.5 WITHIN AND BETWEEN-RUN ACCURACY AND PRECISION

The accuracy of an analytical procedure expresses the closeness of the determined value obtained by the method to the nominal concentration of the analyte (expressed in percentage).

The precision of the analytical method describes the closeness of repeated individual measures of analyte and it is expressed as the coefficient of variation (CV).

Code: GCLP022/01

Page. 20 of 27

- Within-run accuracy and precision will be determined by analyzing in a single run 6 samples per level at 4 level of concentration (LLOQ, LQC, MQC, HQC)
- Between-run accuracy and precision: determined by analyzing in five runs, performed in different days, 3 samples per level at 4 level of concentration (LLOQ, LQC, MQC, HQC).

4.5.1 Procedure

Accuracy and precision are assessed on AHA sample spiked with known amount of analyte, quality control (QC). QC samples are prepared independently from the calibration standards (CC) and are analyzed against the calibration curve.

Prepare working standard solutions and IS working standard solutions as described in § 2.3.1, 2.3.2 and 2.3.3 and the AHA samples as described in § 2.4.1; process AHA samples as described in § 2.4.2. For within-run assay during a single analytical run, inject the samples according to the following sequence:

N.	SAMPLE	N.	SAMPLE
1	Blank	18	LQC 3
2	Zero-blank	19	LQC 4
3	LLOQ 1 (G)	20	LQC 5
4	LLOQ 2	21	LQC 6
5	LLOQ 3	22	MQC 1
6	LLOQ 4	23	MQC 2
7	LLOQ 5	24	MQC 3
8	LLOQ 6	25	MQC 4
9	F	26	MQC 5
10	Е	27	MQC 6
11	D	28	HQC 1
12	C	29	HQC 2
13	В	30	HQC 3
14	Α	31	HQC 4
15	Blank	32	HQC 5
16	LQC 1	33	HQC 6
17	LQC 2		

For between-run assay, for 5 different analytical runs over at least two different days, inject the samples according to the following sequence:

Code: GCLP022/01

N.	SAMPLE	N.	SAMPLE
1	Blank	12	Blank
2	Zero-blank	13	LQC 1
3	LLOQ 1 (G)	14	LQC 2
4	LLOQ 2	15	LQC 3
5	LLOQ 3	16	MQC I
6	F	17	MQC 2
7	Е	18	MQC 3
8	D	19	HQC 1
9	С	20	HQC2
10	В	21	HQC3
11	A		

4.5.2 Calculations

Accuracy: evaluate each point accuracy according to the following formula:

$$\% Acc = \frac{x_j - x_i}{x_i} * 100$$

where:

 x_j = found concentration of j-eme analyte

 x_i = actual concentration of j-eme analyte

Accuracy (%) in within-run assay (mean value of 6) and Accuracy (%) in between-run assay (mean value of 18) should be $\pm 15\%$, except for LLOQ level which should be $\pm 20\%$.

Precision: calculate precision coefficient of variation CV(%), equivalent to relative standard deviation according to USP XXIII, page 1982.

CV% in within-run assay (mean value of 6) and CV% in between-run assay (mean value of 18) should be \leq 15%, except for LLOQ level which should be \leq 20%.

At least 67% of QCs concentration results should be within 15% of their respective nominal values. At least 50% of QCs at each level should be within 15% of their nominal concentration

4.6 MATRIX EFFECT

Matrix effect is evaluated in order to check if the matrix may affect the accuracy of the determination. This determination is performed at a low and at a high level of concentration (LQC and HQC) using matrixes.

Code: GCLP022/01

Page. 22 of 27

4.6.1 Procedure

Analyze LQC level (blank matrix spiked with analytes after extraction) in matrix and at the same level (LQC) in absence of matrix (water/methanol 50/50 (v/v)). Repeat the analysis at HQC level. Using the same approach, Matrix effect is also evaluated in order to verify if oxibuprocaine² (use as anesthetic before the surgical procedure), iodopovidone (use as antimicrobial) and benzalkonium chloride (present in the drug product formulation) affect the determination. Oxibuprocaine, iodiopovidone and benzalkonium chloride levels that should be included in aqueous humor in order to define the matrix effect is defined according to literature. Mean values plus 2 times the standard deviation (SD) is tested.

Benzalkonium chloride (BAK) level found in rabbit aqueous humor after 15 drops of 0.05% BAC dosage [3] is $0.52 \pm 0.13 \,\mu\text{g/mL}$: Considering this value as mean \pm Standard Error (worst case) and being the study performed on 24 eyes, SD is 0.637^3 . According to this approach, BAK is tested at 1.8 $\,\mu\text{g/mL}$ in AHA. This is a worst case if compared to drug product posology in clinical study (2 drops of drug product containing 0.1 $\,\text{mg/mL}$ of BAK).

According to literature [4], lidocaine levels in human aqueous humor after administration of 3 and 6 drops of anesthetic at 4 mg/mL are $1.4 \pm 0.5 \,\mu\text{g/mL}$ and $4.2 \pm 1.5 \,\mu\text{g/mL}$ (Mean \pm SD) respectively. Assuming that the same absorption for oxibuprocaine, it is tested at 7.2 $\mu\text{g/mL}$ in AHA, worst case if compared to anesthetic posology (3 drops).

Iodopovidone (0.5% iodine) is used as antimicrobial and is not instilled inside the eye. It is tested at 7.2 μ g/mL in AHA, assuming an absorption similar to oxibuprocaine (worst case).

Prepare WS 1 containing 2.214 nmol/mL of levofloxacine, 2.038 nmol/mL dexamethasone,1.549 nmol/ mL of dexamethasone 21-phosphate and 1.59 nmol/mL of IS in methanol.

Prepare WS 2 containing 0.042 nmol/mL of levofloxacine, 0.038 nmol/mL dexamethasone, 0.087 nmol/ mL of dexamethasone 21-phosphate and 1.59 nmol/mL of IS in methanol.

Prepare LQC and HQC in solvent diluting 20 μ L of WS with 20 μ L of water (use WS1 for HQC and WS2 for LQC)

Prepare LQC and HQC in matrix (use WS1 for HQC and WS2 for LQC):

Matrix 1: 20 μ L of WS with 20 μ L of AHA

Matrix 2: 20 μL of WS with 20 μL of AHA containing BAK 0.8 μg/mL

² Lidocaine may be considered as backup, in case of oxibuprocaine matrix effect.

³ SD = SE x \sqrt{n} , where n= 24

Code: GCLP022/01

Page. 23 of 27

Matrix 3: 20 μL of WS with 20 μL of AHA containing oxibuprocaine 7.2 μg/mL

Matrix 4: 20 μL of WS with 20 μL of AHA containing iodiopovidone (0.5% iodine) 7.2 μg/mL

Inject the samples as described in the following sequence:

N.	SAMPLE	N.	SAMPLE
1	LQC solvent	13	HQC solvent
2	LQC matrix	14	HQC matrix
3	LQC solvent	15	HQC solvent
4	LQC matrix	16	HQC matrix
5	LQC solvent	17	HQC solvent
6	LQC matrix	18	HQC matrix
7	LQC solvent	19	HQC solvent
8	LQC matrix	20	HQC matrix
9	LQC solvent	21	HQC solvent
10	LQC matrix	22	HQC matrix
11	LQC solvent	23	HQC solvent
12	LQC matrix	24 HQC matrix	

Calculation

Verify, for each level of concentration, the matrix factor (MF) for the analytes and for IS by calculating the ratio of peak area in presence of matrix to the peak area in absence of matrix according to the following formulas:

 $MF_{Analyte} = Analyte$ peak area in presence of matrix / Analyte peak area in absence of matrix $MF_{IS} = IS$ peak area in presence of matrix / IS peak area in absence of matrix

IS normalized MF is also calculated by dividing the MF of analyte by the MF of IS according to the following formula:

IS normalised MF =
$$\frac{MF \ Analyte}{MF \ IS}$$

The CV% of the IS normalized MF at both concentration levels should be lower than 15%.

Code: GCLP022/01

Page. 24 of 27

4.7 RECOVERY EFFICIENCY

Recovery efficiency should be demonstrated by comparison of 6 samples in matrix at LQC and HQC levels with samples prepared in blank matrix spiked with analytes after extraction at the same concentrations.

Recovery of the analytes need not be 100%, but should be consistent, precise and reproducible.

4.8 DILUTION INTEGRITY

Dilution integrity should be demonstrated by spiking the matrix with an analyte concentration above the ULOQ and diluting this sample with blank matrix to obtain a concentration value in the range of calibration curve.

4.8.1 Procedure

1. Dilute 800 μL of Intermediate Solution-2a and -2b (see § 2.3.2) to 10 mL of AHA.

Divide AHA samples into 10 μ L aliquots and use it to validate the dilution factor 1:10 (5 replicates each).

- 1:10 To 10 μ L aliquots add 90 μ L of blank AHA. The final concentration of analytes in in AHA is 2.214 nmol/mL of levofloxacin, 2.038 nmol mL of dexamethasone and 1.936 nmol/mL of dexamethasone 21-phosphate.
- 2. Dilute 800 µL of each Stock Standard Solution-2 (see § 2.3.2) to 10 mL of AHA.

Divide HA samples into 10μ L aliquots and use it to validate the dilution factor 1:100 (5 replicates each).

1:100 \rightarrow To 10 μ L aliquots add 90 μ L of blank AHA. Subsequently dilute 10 μ L of this diluted AHA sample with 90 μ L of blank AHA. The final concentration of analytes in in AHA 2.214 nmol/mL of levofloxacin, 2.038 nmol mL of dexamethasone and 1.936 nmol/mL of dexamethasone 21-phosphate.

4.8.2 Calculation

Recalculate the concentration of AHA samples having a concentration higher than the ULOQ taking into account the dilution factor. Mean accuracy should be $\pm 15\%$ and precision (CV) should be $\leq 15\%$.

4.9 STABILITY

The stability of analytes samples in different conditions are checked

Code: GCLP022/01

Page. 25 of 27

4.9.1 Bench top stability in matrix at room temperature - procedure

Twelve AHA samples spiked at LQC and HQC levels (six per QC level) and two AHA blank samples are prepared and analysed after 6 hours at room temperature. Six spiked samples for each concentration and one blank sample analysed immediately after the preparation. Samples are analysed against a freshly prepared calibration curve.

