9.4.2 ANALYSIS OF THE ENDPOINT

Aqueous humour concentration of levofloxacin and dexamethasone, measured by LC-MS-MS, will be descriptively summarized by treatment group and 95% confidence limits will be provided.

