10.1.4 FUTURE USE OF STORED SPECIMENS AND DATA

Not applicable, samples of aqueous humour will be destroyed after the concentration analyses.

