1 INTRODUCTION

1.1 AIM OF THE STUDY

The aim of this study is to perform a full validation to quantify Levofloxacin, Dexamethasone 21-phosphate and its metabolite Dexamethasone in human aqueous humor to demonstrate that it is suitable for its intended purpose.

Substantially, the method consist of IS addition, precipitation with methanol, then chromatographic separation under gradient conditions and MS/MS detection. The method will be validated to investigate matrix effect, recovery efficiency, within and between-run accuracy, within and between-run precision, linearity, lower limit of quantitation, carry-over effect, dilution integrity, short-term stability in matrix and in frozen matrix, freeze-thaw cycles stability, autosampler stability, to fulfil the requirements of the recently issued EMA's Guideline on bioanalytical method validation [1] and it will be performed in accordance with PRC Ticinum Lab SOPs.

Because the human aqueous humor is a rare matrix and its collection is difficult (since it is only possible by anterior chamber paracentesis), as deviation from EMA's Guideline on bioanalytical method validation [1], method selectivity will be evaluated on a single batch of artificial aqueous humor (AHA) instead on matrix coming from six different sources.

Artificial aqueous humor (AHA) will be recreated and utilised as matrix during the validation study. According to literature [2], no differences in the analysis of ophthalmological drugs were found between artificial and human aqueous humor; thus, the artificial one may be used to generate a matrix-based standard curve for method analytes quantification.

Long-term stability in matrix at -80°C will be also evaluated at 1, 3, 6 and 12 months and the obtained results will be reported in interim reports issued at each time points.

Stability of analytes stock solutions has been already validated by Accelera S.r.l. during the validation studies "Eye Drop combi, Levofloxacin/Dexamethasone Eye Drops Solution: Validation of an Analytical Method for the Determination of Levofloxacin in the Rabbit Aqueous Humor by LC-MS/MS" (Report Study 2017-0050) and "Eye Drop combi, Levofloxacin/Dexamethasone Eye Drops Solution: Validation of an Analytical Method for the Determination of Dexamethasone 21-phosphate and Dexamethasone in the Rabbit Aqueous Humor by LC-MS/MS" (Report Study 2017-0051) and do not need to be re-validated.

Stability of Internal Standard stock solutions will be evaluated.

Code: GCLP022/01

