2.1.2 Reagents

In-vitro artificial aqueous humor:

AHA is prepared by dissolving NaCl (6.19 g/L), KCl (0.39 g/L), CaCl₂ (0.28 g/L), NaHCO₃ (2.90

g/L), glucose (0.80 g/L), Urea (0.10 g/L), albumin (0.10 g/L), Na-lactate (0.28 g/L) and Na-ascorbate (0.15 g/L) in water. Each substance is added separately in the above mentioned order. The solution is to be stirred constantly and kept at room temperature. Na-lactate and Na -ascorbate are added last and the solution is then adjusted at pH 7.21 with HCl 1M. Aqueous humor is centrifuge at 4000 rpm for 1 minute, supernatant is stored at 4°C until

analysis.

1M HCOONH₄:

Weight 6.6 g of HCOONH4 and transfer in a 100 mL graduated flask, then

dilute with H₂O to volume.

Code: GCLP022/01

Page. 12 of 27

10 mM HCOONH₄:

10 mL of 1M HCOONH4 are diluted to 1 L with water

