4.9.2 Freeze/thaw (F/T) stability - procedure

Thirty-six AHA samples spiked at LQC and HQC levels (six per QC level) and three AHA blank samples are prepared, frozen in the freezer at -80°C and thereafter thawed at room temperature. After complete thawing, samples are refrozen again applying the same conditions. At each cycle, sample should be frozen for at least 12 hours before they are thawed. One, two and three cycles are tested. Six spiked samples for each concentration and one blank are analysed immediately after the preparation, six spiked samples for each concentration and for each F/T cycle are analysed against a freshly prepared calibration curve.

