4.9.3 Short-term stability in frozen matrix- procedure

Twelve AHA samples spiked at LQC and HQC levels (six per QC level) and two AHA blank samples are prepared and analysed at the end of the method validation at nominal -80°C. Six spiked samples for each concentration and one blank sample analysed immediately after the preparation. Samples are analysed against a freshly prepared calibration curve.

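### Prodrug stability is tested only in artificial aqueous humour, so conversion that needs human fluid would go unseen; 9.4.2 should also report dexamethasone 21-phosphate and a supplementary molar total

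*Combined protocol and SAP*

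**What the plan says.** The Laboratory Protocol (Appendix 12.1, section 1.1) describes the steroid analytes as "Dexamethasone 21-phosphate and its metabolite Dexamethasone in human aqueous humor", so the two are linked by conversion. The same section fixes the test medium: "Artificial aqueous humor (AHA) will be recreated and utilised as matrix during the validation study". Its recipe (2.1.2) is four salts plus "glucose (0.80 g/L), Urea (0.10 g/L), albumin (0.10 g/L), Na-lactate (0.28 g/L) and Na-ascorbate (0.15 g/L) in water"; no enzyme is listed.

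All five matrix stability tests use spiked AHA:

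- bench top (4.9.1): "two AHA blank samples are prepared and analysed after 6 hours at room temperature"
- freeze/thaw (4.9.2): "Thirty-six AHA samples spiked at LQC and HQC levels (six per QC level) and three AHA blank samples are prepared"
- short-term frozen (4.9.3): "two AHA blank samples are prepared and analysed at the end of the method validation"
- autosampler (4.9.4) and long-term at -80 °C (4.9.5): AHA again

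The twelve blinded quality control samples are also made in synthetic humour (protocol 4.1, 6.3, 8.2).

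On the analysis side, protocol 9.4.2 states: "Aqueous humour concentration of levofloxacin and dexamethasone, measured by LC-MS-MS, will be descriptively summarized by treatment group". The synopsis lists three analytes as the endpoint, including dexamethasone 21-phosphate. Section 3 and 9.4.2 name two and leave the phosphate out. The objective, in both the synopsis and section 3, is the penetration of levofloxacin and dexamethasone 21-phosphate. No sum of the two steroid species appears anywhere.

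**The concern.** A stability test can fail only through processes that its medium can support. AHA would reveal plain chemical hydrolysis of the phosphate. It cannot reveal conversion that depends on something present in human aqueous humour and absent from the recipe. A pass at the ±15% limit (Laboratory Protocol 4.9.6) is therefore silent on that route.

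The reason given for using AHA does not close the gap. The Laboratory Protocol (1.1) cites literature on the analysis of ophthalmological drugs and concludes that AHA may serve for the standard curve. As summarised there, that supports quantification, not prodrug stability. The earlier rabbit validations are relied on only for the stock solutions.

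Dexamethasone formed in the vial cannot be told apart from dexamethasone formed in the eye. If it occurred, the dexamethasone mean would read too high and the phosphate too low. Section 9.4.2 summarises the first and not the second, so a reader of the results could not see the balance between them.

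**Working it through.** **Inputs.** SD 15 ng/ml, n = 40, half-width 4.648 ng/ml (protocol 9.2). Molecular weight of dexamethasone 392.46 g/mol (Laboratory Protocol 1.7.1). Concentrations in AHA from the scheme in 2.4.1: the lowest standard (LLOQ) is 0.058 nmol/mL for the phosphate and 0.013 for dexamethasone. The low QC is 0.087 and 0.038, the medium QC 0.155 and 0.204, and the high QC 1.549 and 2.038, in the same order.

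**1. The plan's precision figure.** 1.95996 × 15 / √40 = 4.6485 ng/ml, against 4.648 stated. It reproduces.

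**2. What the AHA tests can see.** One mole of phosphate yields one mole of dexamethasone. Dexamethasone rises by 15% when the converted fraction is f = 0.15 × dexamethasone / phosphate.

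- Low QC, unrounded: 0.15 × 0.0382 / 0.0871 = 6.6%.
- High QC: 0.15 × 2.038 / 1.549 = 19.7%, so there the 15% limit on phosphate loss is reached first.

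The tests are thus reasonably sensitive to conversion that can happen in AHA. For conversion that cannot happen in AHA, their sensitivity is nil.

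**3. Scale if conversion occurred.** Added dexamethasone (ng/ml) = f × phosphate (nmol/mL) × 392.46. The documents give neither f nor a patient phosphate level, so both are assumed here:

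| Assumed phosphate (nmol/mL) | f = 10% | f = 25% | f = 50% |
|---|---|---|---|
| 0.058 (LLOQ) | 2.3 | 5.7 | 11.4 |
| 0.087 (low QC) | 3.4 | 8.5 | 17.1 |
| 0.155 (medium QC) | 6.1 | 15.2 | 30.4 |

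One planned half-width corresponds to 4.6485 / 392.46 = 0.0118 nmol/mL converted, and 0.0118 / 0.058 is about 20% of the phosphate LLOQ. At f = 0 the shift is zero.

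**4. Effect on the contrast between steroid arms.** With the same f in both arms, the difference in mean dexamethasone shifts by f × (P1 − P2) × 392.46, where P1 and P2 are the mean phosphate levels. This is zero when the phosphate levels agree. Absolute means shift by the full f × P × 392.46.

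**5. The molar total.** Take an assumed 0.10 nmol/mL of each species. At f = 0, 25% and 50%, dexamethasone alone reads 39.2, 49.1 and 58.9 ng/ml. The total stays at 0.20 nmol/mL.

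**6. The cost of the total.** With phosphate below LLOQ, the total is known only to within 0.058 × 392.46 = 22.8 ng/ml dexamethasone-equivalents, which is 22.8 / 4.648 = 4.9 half-widths. Dexamethasone's own LLOQ is 0.013 × 392.46, or about 5 ng/ml. If 8 of 40 patients were below the phosphate LLOQ, the bounds on the arm mean would lie 8/40 × 22.8 = 4.6 ng/ml apart, about one half-width.

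**The case against.** The strongest reply is that nothing in the documents shows drawn aqueous humour converting phosphate in a vial. Calling dexamethasone a metabolite says that conversion happens somewhere after dosing, not that it continues after sampling. Samples go straight to -80 °C (protocol 8.1), and methanolic internal standard is added 1:1 at preparation (Laboratory Protocol 2.3.3, 2.4.2). This stands: the existence of vial conversion is an assumption, as well as its size. What remains is that no maximum time to freezing and no stabiliser is stated, and that thawing and handling before methanol is added are untested in human fluid.

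Four stronger readings are tempting, and the documents do not support them.

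- A reader might infer that steroid penetration would be overstated. Phosphate converted in the vial had already reached the aqueous humour, so only the split moves.
- A reader might take 22.8 ng/ml as a bias estimate. As a shift in dexamethasone it needs full conversion of an assumed phosphate level.
- A reader might think that patient samples stand for 6 hours at room temperature. That is the duration of the validation test; no such hold is planned for patient samples.
- A reader might conclude that the total should replace the named endpoints. Step 6 shows why not: with phosphate below LLOQ, the total can be as uncertain as the problem it addresses.

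It is also fair to say that the phosphate is assayed in every sample, that the synopsis names it as an endpoint and that listings are planned (9.4.7), so a total could be derived later. That makes the change easy; it does not make it part of the planned summary. The analysis is descriptive (9.1), so no decision threshold is at risk.

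**Conclusion.** The point holds as a gap in verification and a cheap improvement to the analysis. Prodrug stability is shown only in a medium with no listed enzyme, so conversion dependent on human matrix would pass unseen. Its occurrence and size are unknown: the shift could be nil, or could reach one planned half-width with as little as 0.0118 nmol/mL converted. Any effect falls on the division between prodrug and dexamethasone, and on absolute dexamethasone levels more than on the contrast between the steroid arms. The limit on that last statement is that phosphate levels and handling times must be similar in the two arms. Independently of conversion, 9.4.2 leaves out the species that the objective names.

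**What to change.** In protocol 9.4.2:

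- Summarise dexamethasone 21-phosphate by arm as well, which also brings the section into line with the synopsis.
- Add a supplementary per-patient total, dexamethasone + dexamethasone 21-phosphate in nmol/mL, summarised for the two steroid arms with 95% confidence limits. Place it next to the named endpoints, not in their stead.
- When the phosphate is below LLOQ, show the total at both bounds (phosphate 0 and 0.058 nmol/mL) and give the number of patients concerned.

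In the study report, state that stability of the prodrug was not verified in human aqueous humour.

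The cost is one derived variable, a few table rows and a sentence. Both analytes are already measured and calibrated in molar units, so no new sampling or assay is needed. The downside is the coarse phosphate LLOQ: the total is informative mainly where the phosphate is quantifiable.

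A spike test in leftover patient fluid is not part of this recommendation. Choosing levofloxacin-arm vials would need allocation information while labels carry only kit numbers, the drawn volume is only approximate, and 10.1.4 provides that "samples of aqueous humour will be destroyed after the concentration analyses".
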